7. Radiographs to be read centrally. Previous radiographs (up to 2 years old) of the SI joints documenting the diagnosis of AS will be acceptable if they can be obtained and sent to the central reader for confirmation. If radiographs are not available or cannot be interpreted by the central reader, new radiograph (AP pelvis) should be obtained during the screening period and submitted to the central reader.
8. The lipid panel will include apolipoprotein A-1 and B, total cholesterol, HDL, LDL, and triglycerides. Other lipoprotein tests potentially include particle size measurements.
9. Urine pregnancy test is required only for WOCBP; may be repeated more frequently if required by local regulation/practice, if a menstrual cycle is missed, or if a potential pregnancy is suspected.
10. Women of non-childbearing potential must meet one of the following criteria: undergone hysterectomy and/or bilateral oophorectomy, medically confirmed

Protocol Activity Visit Window (days)	Screening ¹	Treatment Period										Follow -up ¹¹
	30 days	Baseline Day 1	Week 2	Week 4	Week 8	Week 12	Week 16	Week 24	Week 32	Week 40	Week 48	
			±3	±3	±7	±7	±7	±7	±7	±7	±7	±7

ovarian failure or confirmed to be post-menopausal (cessation of regular menses for at least 12 consecutive months with no alternative pathological or physiological cause); status may be confirmed with/and have a central laboratory confirmation of FSH level indicative of postmenopausal state.

11. The Follow-up Visit is required of all subjects who complete the study or are withdrawn from the investigational product after the Week 40 visit. These subjects must have a Follow-up visit within 28 days (±7 days) of the Week 48 visit. Subjects who are withdrawn from the investigational product prior to the Week 40 visit are not required to have a follow-up visit after they complete the study at the Week 48 visit.

12. hsCRP will be blinded after the Screening visit.

14. Qualified blinded assessor (blinded to previous assessments both of efficacy and safety) must be used. It is recommended that the same qualified personnel be used for each visit.

15. The combined index score will be calculated by the Sponsor using the individual scores from the following measures: lateral spinal flexion, tragus-to-wall distance, lumbar flexion (modified Schober), maximal intermalleolar distance, and cervical rotation.

16. Chest expansion will be measured for spinal mobility.

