5.4.2. Preparation and Dispensing

The investigational product will be dispensed using an IRT drug management system at each visit from Baseline to Week 40 (excluding Week 2). A qualified staff member will dispense the investigational product via unique container numbers in the bottles provided, in quantities appropriate for the study visit schedule. The subject/caregiver should be instructed to

maintain the product in the bottle provided throughout the course of dosing and return the bottle to the site at the next study visit.

The investigational product will be packaged and labeled in such a manner that the subject and study staff will be unable to determine from the dispensed packaging to which treatment arm the subject is assigned during the double-blind treatment period. At study visits sufficient investigational product will be dispensed to complete dosing until the next scheduled visit. The amount of investigational product dispensed at each visit must be recorded. At study visits the subject must return all investigational product and the amount of investigational product returned will be recorded to account for all dispensed investigational product.

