- Laboratory testing: Central laboratory tests include: Hematology, Urinalysis, Chemistry Panel, Lipid Profile (fasting), Urine Pregnancy Test (for women of childbearing potential only), hsCRP;
- Blood sample for FACS Analysis;
- Complete Physical Examination: General appearance, skin (presence of rash), HEENT (head, eyes, ears, nose and throat), lungs (auscultation), heart (auscultation for presence of murmurs, gallops, rubs), lower extremities (presence of peripheral edema), abdominal (palpation and auscultation), neurologic (mental status, station, gait, reflexes, motor and sensory function, coordination) and lymph nodes;
- Weight (without shoes preferred);
- Specific Medical History: History of uveitis, psoriasis, inflammatory bowel disease and peripheral articular involvement as assessed by swollen joint count;
- BASMI (linear function) by qualified blinded assessor: Lateral spinal flexion, tragus-to-wall distance, lumbar flexion (modified Schober), maximal intermalleolar distance and cervical rotation;
- Spinal mobility obtained by qualified blinded assessor: chest expansion;
- Assessment of swollen joints (44-joint count) by qualified blinded assessor;

- Assessment of enthesitis using the MASES Index by qualified blinded assessor;
- Administer in-clinic dose of investigational product from previously dispensed study drug supplies;
- Complete drug accountability;
- Contraception check: Confirm and document that proper contraception is being used;
- Risk factor check for VTE ([Section 7.1.14](#));
- Monitoring of adverse events and concomitant treatments. Record any modifications, deletions or additions.

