6.3. Follow-up Visit

The Follow-up visit is required of all subjects who complete the study or are withdrawn from the investigational product after the Week 40 visit. These subjects must have a Follow-up visit within 28 days (± 7 days) of the Week 48 visit. Subjects who are withdrawn from the investigational product prior to the Week 40 visit are not required to have a follow-up visit after they complete the study at the Week 48 visit. There is a ± 7 day window for this visit.

All subjects who complete or discontinue early from the investigational product after Week 40 must have a Follow-up visit within 28 days (± 7 days) of the Week 48 visit.

Subjects are required to fast for at least 9 hours prior to the visit; however, blood collection for laboratory testing may be taken up to 48 hours prior to or following this visit as necessary to ensure the samples are collected in a fasting state.

The following procedures will be performed:

- Targeted physical examination (examination of heart, lungs, abdomen, lower extremities, skin (presence of rash) and lymph nodes);
- Weight (without shoes preferred);
- Specific Medical History: History of uveitis, psoriasis, inflammatory bowel disease and peripheral articular involvement as assessed by swollen joint count;
- Vital Signs and temperature: Blood pressure (seated), pulse rate and temperature (via tympanic, oral or temporal, preferred);
- Laboratory testing: Central laboratory tests include: Hematology, Urinalysis, Chemistry Panel, Lipid Profile (fasting), Urine Pregnancy Test (for women of childbearing potential only), hsCRP;
- Adverse event reporting and concomitant treatment use;

- Risk factor check for VTE ([Section 7.1.14](#));
- Contraception check: Confirm and document that proper contraception is being used.

If abnormalities in hematology or chemistry results or adverse events with a causal relationship to the study medication are still observed/ongoing at the follow-up visit, the subject must continue to be followed until the laboratory abnormality or adverse event stabilizes or returns to baseline levels as approved by the Sponsor.

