8.1.2. Eliciting Adverse Event Information

The investigator is to record on the CRF all directly observed AEs and all AEs spontaneously reported by the study subject. In addition, each study subject will be questioned about the occurrence of AEs in a non-leading manner.

8.1.3. Withdrawal due to Adverse Events (see also the [Subjects Discontinuation from the Investigational Product](#) section)

Withdrawal due to AEs should be distinguished from withdrawal due to other causes, according to the definition of AE noted below, and recorded on the CRF.

When a subject withdraws from the investigational product because of an SAE, the SAE must be recorded on the eCRF and reported, as appropriate, on the CT SAE Report Form, in accordance with the [Requirements](#) section above.

Subjects that are withdrawn due to an AE will remain in the study and must continue to be followed for protocol specified follow-up procedures. The only exception to this is when a subject specifically withdraws consent for any further contact with him or her or persons previously authorized by the subject to provide this information. In this case, no further evaluation should be performed, and no additional data should be collected. The sponsor may retain and continue to use any data collected before such withdrawal of consent.

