8.1.4. Time Period for Collecting AE/SAE Information

The time period for actively eliciting and collecting AEs and SAEs (“active collection period”) for each subject begins from the time the subject provides informed consent, which is obtained before the subject’s participation in the study (ie, before undergoing any

study-related procedure and/or receiving investigational product), through and including a minimum of 28 calendar days after the last administration of the investigational product.

For subjects who are screen failures, the active collection period ends when screen failure status is determined.

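### The Follow-up window of 28 ± 7 days lets the last scheduled contact fall up to 7 days before the required 28 days of active AE/SAE collection are complete

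*Protocol*

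**What the plan says.** Protocol Section 8.1.4 runs the active collection period from informed consent "through and including a minimum of 28 calendar days after the last administration of the investigational product". Section 8.1.2 makes this more than passive recording: "each study subject will be questioned about the occurrence of AEs in a non-leading manner".

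The end-of-study schedule is as follows.

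- **Last dose.** Section 5.4.2 reads: "The investigational product will be dispensed using an IRT drug management system at each visit from Baseline to Week 40 (excluding Week 2"). Nothing is dispensed at Week 48. The Week 48 procedures in Section 6.2.10 include "Administer in-clinic dose of investigational product from previously dispensed study drug supplies". For a completer, that dose is the last.
- **Follow-up visit.** Footnote 11 of the Schedule of Activities states: "The Follow-up Visit is required of all subjects who complete the study or are withdrawn from the investigational product after the Week 40 visit". Section 6.3 gives the timing as "These subjects must have a Follow-up visit within 28 days (± 7 days) of the Week 48 visit" and then repeats it: "All subjects who complete or discontinue early from the investigational product after Week 40 must have a Follow-up visit within 28 days", again with ±7 days. The Follow-up column of the Schedule and the duration text in Section 3 carry the same tolerance.
- **After the Follow-up visit.** Section 6.3 prolongs contact only when laboratory abnormalities or causally related events "are still observed/ongoing at the follow-up visit, the subject must continue to be followed until the laboratory abnormality or adverse event stabilizes".

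Subjects who stop product before Week 40 are excused the Follow-up visit but are still seen at Week 48. Section 13.1 ends the trial at the last visit of the last subject.

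**The concern.** The two rules use different anchors and different limits. The safety rule counts from the last dose and sets a floor of 28 days. The visit rule counts from the Week 48 visit and allows a week either side of 28 days. For a completer the anchors coincide, so the early half of the visit window lies wholly below the floor.

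A site can therefore follow the Schedule exactly and still have no planned occasion to ask about an event that begins on, say, Day 24. The continuation rule in Section 6.3 does not help, because such an event is not yet present at a Day 21 visit. Meeting Section 8.1.4 then depends on a contact that the protocol does not name, or on the subject volunteering the event. If the last subject happens to be seen early, Section 13.1 lets the trial formally close before that subject's 28 days are up.

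What is at stake is completeness of safety ascertainment at the end of exposure, and consistency of that ascertainment between subjects. Efficacy is not at stake.

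**Working it through.** **Inputs**

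- Required end of active collection: Day 28 after the last dose, inclusive (Section 8.1.4).
- Follow-up visit: 28 ± 7 days from the Week 48 visit (Section 6.3, footnote 11, Schedule of Activities, Section 3).
- Completer's last dose: at the Week 48 visit (Sections 5.4.2 and 6.2.10).
- Target days: Week 40 = Day 281, Week 48 = Day 337 (SAP Table 5). Both visits have ±7-day windows (Schedule of Activities).

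**The plan's own figure.** Section 3 gives about 56 weeks of participation. 30 + 16×7 + 32×7 + 28 = 394 days, and 394/7 = 56.3 weeks. This reproduces, so the nominal plan does contain a 28-day follow-up. Only the minus side of the tolerance is in question.

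**Shortfall formula.** Let k be the days from the last dose to the Week 48 visit.

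- Earliest in-window Follow-up visit = k + 28 − 7 = k + 21 days after the last dose.
- Largest shortfall = max(0, 28 − (k + 21)) = max(0, 7 − k).

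**Completers (k = 0).** The window is Days 21 to 35, which is 15 permitted days. Days 21 to 27, which is 7 of the 15, precede Day 28. The shortfalls on those days are 7, 6, 5, 4, 3, 2 and 1, and they are 0 from Day 28 on. The maximum is 7/28 = 25% of the period.

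The documents give no distribution of visit dates. If visits were spread evenly over the window (an assumption), the mean shortfall would be 28/15 = 1.87 days, or 6.7% of 28 days. The possible range is 0 (all visits on or after Day 28) to 7 days (all on Day 21).

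**Subjects stopping shortly before Week 48**

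| k (days) | Earliest visit (days after last dose) | Largest shortfall (days) | Even-spread mean (days) |
|---|---|---|---|
| 0 | 21 | 7 | 1.87 |
| 1 | 22 | 6 | 1.40 |
| 2 | 23 | 5 | 1.00 |
| 3 | 24 | 4 | 0.67 |
| 4 | 25 | 3 | 0.40 |
| 5 | 26 | 2 | 0.20 |
| 6 | 27 | 1 | 0.07 |
| 7 | 28 | 0 | 0 |

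The cut-off at fewer than 7 days is exact.

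**Subjects stopping before Week 40.** The smallest gap from a Week 40 visit to a Week 48 visit is (337 − 7) − (281 + 7) = 42 days, 14 more than needed. They are unaffected.

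**Literal reading.** If *within 28 days* is taken as an upper limit only, the visit has no lower bound and the gap could be larger. The figures above use the more generous reading, Days 21 to 35.

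**After the change.** With −0/+7, the earliest visit is Day 28 after Week 48, and the last dose is never later than Week 48. The shortfall is 0 for every k.

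**The case against.** The best counter-argument is that the two sections do not contradict each other. Section 8.1.4 is a standing duty tied to the last dose, and Section 6.3 merely books a clinic visit. A site that sees a subject on Day 21 and stops asking is in breach of Section 8.1.4, whatever the visit window says. The introduction to the Schedule of Activities allows unplanned visits. Section 8.1.4.1 requires SAEs in the active period to be reported, and later ones when the investigator learns of them. Subjects carry a contact card (Section 4.4.7). The nominal visit day already meets the floor.

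The consequences are also slight. Between-arm risk ratios for adverse events cover Baseline to Week 16 only (SAP Section 6.6.1), and the half-life is about 3 hours (Section 1.2.4). The VTE checks under Amendment 3 start at Week 32, which suggests that enrolled subjects may already be late in the trial. A further amendment may not come, and a reminder to sites could serve.

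Most of this stands as a limit on the harm. It confines the likely loss to non-serious or unvolunteered events starting in at most seven days. It does not remove the gap: none of these provisions schedules a question about new events after an early in-window visit. The end-of-trial point adds little, since it can matter only for the last subject or subjects and does not cancel the Section 8.1.4 duty. The even-spread mean is only illustrative. The 0 to 7 day range is what the documents support.

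**Conclusion.** The concern holds. For completers, and for subjects who stop product fewer than 7 days before the Week 48 visit, the protocol permits its last scheduled contact before its own minimum period of active AE/SAE collection has ended. The largest shortfall is 7 − k days: 7 of 28 for completers, 1 at k = 6, none from k = 7.

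This rests on three things: the Week 48 in-clinic dose being a completer's last, the window being read as Days 21 to 35, and no contact being scheduled after the Follow-up visit. How often it would occur cannot be judged without the visit dates.

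The practical impact is small and purely a matter of safety ascertainment. The change is worth making because it is cheap and makes the schedule deliver what Section 8.1.4 demands.

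**What to change.** Preferred: set the Follow-up visit at 28 days (−0/+7) after the Week 48 visit, and replace *within* by *after*. Make the change in both timing sentences and the window line of Section 6.3, in footnote 11, in the Follow-up column of the Schedule of Activities, and in the duration text of Section 3.

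Alternative: keep ±7 days, and require a telephone AE contact on or after Day 28 post-last-dose whenever the visit falls earlier.

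The waiver for subjects who stop before Week 40 can stay as it is.

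The cost is wording in two sections, one footnote and one table column, plus slightly less scheduling freedom or an occasional telephone call. Because amendments need IRB/EC approval (Section 12.1), this should go with the next amendment rather than be issued alone.

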6.4. Subjects Discontinuation from the Investigational Product

Subjects may discontinue from the investigational product at any time at their own request, or they may be withdrawn from the investigational product at any time at the discretion of the investigator or sponsor for safety (see also the [\(Monitoring Criteria/Discontinuation Criteria \(from the Investigational Product\)\)](#) or the [Withdrawal due to Adverse Events](#)) or behavioral reasons, or the inability of the subject to comply with the protocol required schedule of study visits or procedures at a given study site. Subjects who discontinue the investigational product early should continue to be followed for all regularly scheduled visits for safety and efficacy assessments. Those subjects that discontinue from the investigational product prior to Week 40 visit will not be required to have a follow-up visit.

Per Amendment 3, for subjects with suspected VTE, treatment with tofacitinib should be temporarily withheld while the subject is evaluated. If VTE is confirmed, discontinue treatment with tofacitinib [see Section 6.4.2, Discontinuation Criteria (from the Investigational Product)].

Lost to Follow-up:

If a subject does not return for a scheduled visit, every effort should be made to contact the subject. Withdrawal due to a subject being no longer willing to participate in the study should be distinguished from withdrawal due to “lost to follow-up” (LTFU). Every effort should be made to identify and contact subjects who are potentially LTFU. A subject should not be considered a withdrawal due to LTFU until at least 3 attempts to contact the subject by multiple methods (conducted in accordance with local rules and regulations) have been unsuccessful. All methods of attempted contact with the subject must be clearly documented in the subject’s source documents and the eCRF. All potential LTFU subjects must be discussed with the study team or designee prior to assigning LTFU status.

In any circumstance, every effort should be made to document subject outcome, if possible. The investigator should inquire about the reason for withdrawal, request the subject to return all unused investigational product(s), request the subject to return for a final visit, if applicable, and follow-up with the subject regarding any unresolved adverse events (AEs).

Withdrawal of Consent:

If the subject withdraws from the investigational product, and also withdraws consent for disclosure of future information, no further evaluations should be performed, and no additional data should be collected. The sponsor may retain and continue to use any data collected before such withdrawal of consent.

If a subject has any clinically significant, treatment-emergent, abnormalities at the conclusion of the study, the Pfizer Medical Monitor (or designated representative) should be notified and every effort should be made to arrange follow-up evaluations at appropriate intervals to document the cause of the abnormality. All abnormal laboratory events of clinical significance should be followed until the laboratory values have returned to normal or baseline levels.

6.4.1. Monitoring Criteria

The following laboratory abnormalities require prompt retesting, ideally within 3- 5 days:

- Any single hemoglobin value that drops >2 g/dL (or 20 g/L) below baseline, if indicated after review by the Pfizer Medical Monitor or investigator. Factors that will be considered include stability of hemoglobin values, and their relationship to the standard reference range;
- Absolute neutrophil count $<1.2 \times 10^9/L$ ($<1200/mm^3$);
- Absolute lymphocyte count $<0.5 \times 10^9/L$ ($<500/mm^3$);
- Platelet count $<100 \times 10^9/L$ ($<100,000/mm^3$);
- Serum creatinine increase $>50\%$ over the average of screening and baseline values OR an absolute increase in serum creatinine >0.5 mg/dL (or 44 $\mu\text{mol/l}$) over the average of screening and baseline values, if indicated after review by the Pfizer Medical Monitor or investigator. Factors that will be considered include stability of the creatinine values, and their relationship to the standard reference range;
- Any creatine kinase (CK) $>5x$ upper limit of normal (ULN) (repeat laboratory testing should also include cardiac troponin).

If the abnormality is confirmed after re-test, follow-up should be discussed with the Sponsor and frequency of monitoring increased. Confirmation should be done based upon central laboratory results, but local laboratory results will be acceptable, particularly if these may be done more promptly.

For additional laboratory abnormalities that require prompt retesting, preferably within 48 hours from awareness of the abnormal results see [Section 8.3.2](#) Potential Cases of Drug-Induced Liver Injury.

6.4.2. Discontinuation Criteria (from the Investigational Product)

The investigational product will be discontinued in the event of any of the following:

- Serious infections, defined as any infection (viral, bacterial, and fungal) requiring parenteral antimicrobial therapy or hospitalization for treatment, or meeting other criteria that require the infection to be classified as a serious adverse event;
- Two sequential absolute neutrophil counts $<1.0 \times 10^9/L$ ($<1000/mm^3$);
- Two sequential absolute lymphocyte counts <500 lymphocytes/ mm^3 ;
- Two sequential hemoglobin values <8.0 g/dL (80 g/L) or decreases of $>30\%$ from baseline value;

- Two sequential platelet counts $<75 \times 10^9/L$ ($<75,000/mm^3$);
- Two sequential AST or ALT elevations ≥ 3 times the upper limit of normal with at least one total bilirubin value ≥ 2 times the upper limit of normal;¹
- Two sequential AST or ALT elevations ≥ 3 times the upper limit of normal accompanied by signs or symptoms consistent with hepatic injury (eg, new onset elevated PT/INR);¹
- Two sequential AST or ALT elevations >5 times the upper limit of normal, regardless of total bilirubin or accompanying signs or symptoms;¹
- Two sequential increases in serum creatinine $>50\%$ AND an absolute increase in serum creatinine >0.5 mg/dL ($44 \mu\text{mol/L}$) over the average of screening and baseline values;
- Two sequential creatine kinase (CK) elevations >10 times the upper limit of normal, unless the causality is known not to be medically serious (eg, exercise or trauma induced);
- A confirmed positive urine pregnancy test in a woman of childbearing potential;
- Any opportunistic infections considered significant by the investigator or the Sponsor;
- Requirement of rescue medication for more than 10 consecutive days;
- Subjects interrupting investigational product for more than 5 consecutive days during the double-blind portion or 28 consecutive days during the open-label treatment period or subjects who are less than 80% compliant with the dosage regimen for any two consecutive visit periods;
- Other serious or severe adverse events, in the opinion of the investigator or sponsor. Whenever possible, the investigator should consult with a member of the study team before discontinuation of the subject from the investigational product;
- If VTE is confirmed, discontinue treatment with tofacitinib.

1. In each case, there is a need for additional investigations, such as review of ethanol, recreational drug and dietary supplement consumption; testing for acute hepatitis A, B or C infection and biliary tract imaging should be promptly discussed with the Sponsor or designee.

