4.4.5. Elective Surgery

During the course of this study, elective surgery should be delayed until the end of the placebo-controlled period. No elective surgery should be scheduled without first consulting with the Pfizer Medical Monitor.

Subjects who do require surgery should temporarily discontinue investigational product for one week prior to the surgical procedure and remain off investigational product after the surgical procedure until sutures/staples are removed. If absorbing sutures or chemical closure methods are utilized, investigational product can be resumed when the operative site is sufficiently healed and risk of infection is minimal.

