5.5. Administration

Investigational product will be dispensed to subjects to self-administer after appropriate training and specific instructions are provided. Instructions on dosing will be provided on the Subject Dosing Card. At all visits, the scheduled dose of investigational product will be taken by the subject in the clinic. At the end of each visit, sites will instruct subjects, when to take their investigational product prior to their next study visit. [REDACTED]

[REDACTED] Subjects should receive open-label investigational product at the Week 16 visit and should receive the first dose of the open-label investigational product at the clinic.

Tofacitinib tablets or matching placebo for oral administration may be taken with or without food. Subjects will swallow the investigational product whole, and will not manipulate or chew the investigational product prior to swallowing.

Subjects will be instructed to take their tablet investigational product twice daily (once in the morning and once in the evening approximately 12 hours apart) for a total of two tablets per day. Placebo tablets will match the 5 mg tablets in order to maintain the blind.

During the double-blind treatment period, if the investigator deems it necessary to withhold the investigational product to treat a non-serious infection or other medical condition, temporary withholding is permitted for up to 5 days. If temporary withholding of the investigational product exceeding 5 days is required for a medical reason (eg, elective surgery), the investigator must contact the Pfizer Medical Monitor for approval.

Temporary withholding of the investigational product, as described above, is permitted once during the study without obtaining prior approval from the Pfizer Medical Monitor. Any additional request(s) for temporary withholding of the investigational product during the double blind period require(s) documented approval by the Pfizer Medical Monitor.

Per Amendment 3, for subjects with suspected VTE, treatment with tofacitinib should be temporarily withheld while the subject is evaluated. If VTE is confirmed, discontinue treatment with tofacitinib (see Section 6.4: Subjects Discontinuation from the Investigational Product).

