During the open-label period of the study, tofacitinib 5 mg BID may be temporarily discontinued for up to 28 consecutive days for laboratory abnormalities, for infections which do not meet criteria for serious infections (those requiring parenteral antimicrobial therapy or hospitalization), for surgical procedures or other moderately severe AEs. If treatment must be discontinued for more than 28 days, the subject should be withdrawn from the investigational product permanently (see [Section 6.4.2](#)).

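### Protocol 6.4.2 makes any double-blind interruption over 5 days a mandatory stop, contradicting the approved holds in 5.5 and the surgery hold with resumption in 4.4.5

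*Protocol*

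**What the plan says.** Protocol 6.4.2 opens its list in mandatory terms: "The investigational product will be discontinued in the event of any of the following". One criterion is "Subjects interrupting investigational product for more than 5 consecutive days during the double-blind portion or 28 consecutive days during the open-label treatment period". Nothing in that bullet mentions approval or refers to another section. The creatine kinase criterion in the same list does state an exception: "unless the causality is known not to be medically serious".

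Protocol 5.5 allows one double-blind hold of up to 5 days without prior approval. For a longer one, where withholding "exceeding 5 days is required for a medical reason (eg, elective surgery), the investigator must contact the Pfizer Medical Monitor for approval". The paragraph describes this as temporary withholding. For the open-label period 5.5 sets a firm limit and refers the reader to 6.4.2: "If treatment must be discontinued for more than 28 days, the subject should be withdrawn from the investigational product permanently".

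Protocol 4.4.5 says patients who need surgery "should temporarily discontinue investigational product for one week prior to the surgical procedure and remain off investigational product after the surgical procedure", until sutures or staples are out. With absorbable sutures or chemical closure, "investigational product can be resumed when the operative site is sufficiently healed and risk of infection is minimal".

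**The concern.** The same patient can be entitled to resume under 5.5 and 4.4.5 and bound to stop for good under 6.4.2. A site that applies 6.4.2 literally ends treatment for someone the dosing sections would let back on drug. A site that follows 5.5 can be cited for breaching a stopping rule.

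The choice also reaches the primary endpoint. SAP 2.1.1 (Estimand 1) counts a patient who discontinues product before Week 16 as a non-responder. SAP 9.1 ends on-drug data at the permanent discontinuation date on the End of Treatment CRF page. The SAP rule itself is clear, because a hold followed by resumption creates no cut. The conflict lies in the conduct decision that produces the CRF entry.

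**Working it through.** **Is a 6.4.2 stop permanent?** Yes. The open-label paragraph of 5.5 cites 6.4.2 when it speaks of permanent withdrawal, so 6.4.2 cannot be read as another temporary hold.

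**Rules side by side**

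| Situation | 5.5 / 4.4.5 | 6.4.2 | Agree? |
|---|---|---|---|
| Double-blind hold, up to 5 days | Temporary | Not triggered | Yes |
| Double-blind hold over 5 days, approved | Temporary, may resume | Mandatory stop | No |
| Double-blind surgery hold | At least 7 days, then may resume | Mandatory stop | No |
| Open-label hold over 28 days | Permanent withdrawal (5.5) | Mandatory stop | Yes |

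The pre-operative hold alone is 7 days, and 7 > 5. The limit is passed on day 6, before surgery and before any post-operative days are added. The 5.5 conflict is confined to the double-blind half of the bullet. In the open-label period a surgery hold collides with 6.4.2 only if it runs past 28 days.

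**Stated power reproduced.** Protocol 9.1 assumes 40% on placebo, a 20-point difference, 120 per arm and two-sided 5%, and states about 89% power. With unpooled variance:

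- SE = √[(0.6×0.4 + 0.4×0.6)/120] = √(0.48/120) = 0.0632
- Power = Φ(0.20/0.0632 − 1.96) = 88.5%

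A pooled null variance gives 87.7%. Both are close to the stated figure.

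**Effect of wrongly stopped tofacitinib responders.** The design rates imply 0.60×120 = 72 and 0.40×120 = 48 responders. The test is unstratified and unpooled: z = (p_T − p_P)/√[p_T(1−p_T)/120 + p_P(1−p_P)/120]. Each reclassified responder costs 1/120 = 0.83 points.

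| Tofacitinib responders lost | Counts | Difference | z | Two-sided p |
|---|---|---|---|---|
| 0 | 72 vs 48 | 20.0 | 3.16 | 0.0016 |
| 1 | 71 vs 48 | 19.2 | 3.03 | 0.0025 |
| 8 | 64 vs 48 | 13.3 | 2.09 | 0.037 |
| 9 | 63 vs 48 | 12.5 | 1.96 | 0.0503 |

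Nine is 9/72 = 12.5% of tofacitinib responders, with none lost on placebo.

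**Symmetric version.** Because the holds are managed blind, losses in both arms are more realistic. The documents give no frequency, so assume a fraction f of each arm is stopped this way and counted as non-response. The rates become 0.6(1−f) and 0.4(1−f).

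| f | Unpooled power |
|---|---|
| 0 | 88.5% |
| 1% | 87.9% |
| 2% | 87.2% |
| 3% | 86.5% |
| 5% | 85.1% |
| 10% | 81.3% |

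**The case against.** The best reply is that 5.5 is the specific rule and implicitly qualifies the general list in 6.4.2. Protocol 5.3 supports this: for holds due to an adverse event, infection or elective surgery within protocol limits, it has withdrawal assessed rather than imposed. That is probably the intent. But 5.3 is written for the compliance rule, and 6.4.2 does not defer to 5.5, although the same list spells out an exception where one was wanted.

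A second point is that harm is unlikely. A double-blind hold over 5 days needs contact with the Medical Monitor, and so does scheduling elective surgery. A site that has just obtained approval will seldom then stop the patient. Exclusion 24 bars planned elective surgery, and 4.4.5 says "elective surgery should be delayed until the end of the placebo-controlled period". Unplanned surgery often leaves no room for a full week off drug. Serious infections stop drug under their own criterion. All of this stands, and it is why the impact is rated minor.

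Third, the proposed clause leaves other matters open:

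- The compliance half of the same bullet has no exception. In a 28-day period, 80% compliance allows 0.20×28 = 5.6 missed days, so a long hold straddling a visit could fail two periods running. The case-by-case wording in 5.3 largely covers this.
- Approved double-blind holds have no upper limit.
- A patient on an approved hold at Week 16 would count as on-drug under SAP 9.1.

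The last two are features of the current plan that the clause does not create.

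**Conclusion.** The concern holds. For the double-blind period, 6.4.2 contradicts 5.5 and 4.4.5, and both cannot be followed literally for the same patient. The rule is wrong as written and should be corrected, but it does not threaten the primary result. One affected tofacitinib responder costs 0.83 points. Overturning significance at the design rates needs nine, all on tofacitinib. With symmetric losses of 1% to 2%, power falls by about 1 point or less.

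These figures assume the design response rates and an unstratified test, and no hold frequency is known. Patients who stop product stay in follow-up under Protocol 6.4, and Estimand 2 uses their data without forcing a non-response, so a supportive analysis is already in place.

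**What to change.** In the 6.4.2 bullet, directly after the 5-day double-blind limit, add: *unless the longer hold was approved by the Medical Monitor under Section 5.5 (including surgery holds under Section 4.4.5)*. Unapproved holds over 5 days would still lead to discontinuation. Leave the 28-day open-label limit as it is.

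The cost is one clause in the protocol. The SAP needs no change, and no patients, visits or data are added.
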